**03.09.2025**

## STUDY PROTOCOL

### SHORT CHAIN FATTY ACIDS PROFILES IN AMYOTROPHIC LATERAL SCLEROSIS: LONGITUDINAL EFFECTS OF DISEASE AND MEDITERRANEAN DIET INTERVENTION

**WP1 – Creation of the study design, informed consent for patients, definition of the study population and approval of the protocol**

WP1	Objectives	Status
Deliverables	Establishment of the study protocol	Completed
	Ethics Committee approval	
	Informed consent form	Completed

**WP2 - Determination of the reagents/materials needed at all stages of the research and initiation of procurement procedures**

WP 2	Objectives	Status
Deliverables	Establishing the reagents and materials needed for the research stages (list of necessary materials and equipment, with technical specifications)	Completed
	Establishing the working protocol for neurophysiological exploration	
	Commencement of procurement procedures, contact with suppliers	Completed

**WP3 - Inclusion of patients in the study, initial visit (T0), clinical evaluation, neurophysiological evaluation, collection of biological samples and SCFA analysis (SCFAGGYC-PROF)**

WP 3	Objectives	Status

Deliverables	Identification of patients with ALS (n=44) and healthy controls (similar age and gender; n=40)	Achieved
	Explaining the objectives of the study and signing the informed consent form	Completed
	Clinical and neurophysiological assessment of each ALS patient, with completion of each patient's medical record (including ALSFRS-R)	Completed
	Collection of serum samples	Completed

**WP4 - Reassessment of ALS patients after 6 months (visit T1): clinical and neurophysiological evaluation, collection of biological samples and SCFA analysis, and introduction of the diet**

WP 4	Objectives: Dissemination of research data within the grant	Status
Deliverables	Clinical and neurophysiological assessment of each ALS patient and application of the dietary questionnaire	Completed
	Collection of serum samples	Completed
	Completion of the patient's medical file	Done
	Introduction of a dietary plan	Done

**WP5 - Final reassessment of ALS patients (visit T2): clinical assessment, neurophysiological assessment, collection of biological samples and SCFA analysis**

WP 5	Objectives	Status
Deliverables	Clinical and neurophysiological assessment of each ALS patient 6 months after introduction of the diet	Achieved
	Serum sample collection	Completed
	Completion of each patient's medical file	Completed
	Neurophysiological report	Done

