### WP6 - Serum analysis to identify serum SCFA levels

WP 6	Objectives: Analysis of stored plasma samples using specific analysis kits	Status
Deliverables	Plasma analysis sheets for the SCFAGGYC-PROF profile through the analysis of stored plasma samples  Data entry into the database	Completed

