### WP 7 - Statistical analysis of collected data

WP 7	Objectives: Statistical analysis of clinical, paraclinical and electrophysiological data for each ALS patient compared to the control group	Status
Deliverables	Discovery of the SCFAGGYC-PROF profile in ALS patients at T0 compared to the control group;  Discovery of the SCFAGGYC-PROF profile P-ALS in T0 and T1 evolution;  Identification of changes in the dynamics of the SCFAGGYC-PROF profile in ALS patients comparing T0 with T2.	Achieved

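### WP7 lists no T1–T2 SCFA change, the only interval on the diet; the one listed contrast that reaches T2 also counts six months before the diet

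*Combined protocol and SAP*

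**What the plan says.** The study title promises "LONGITUDINAL EFFECTS OF DISEASE AND MEDITERRANEAN DIET INTERVENTION", so the diet is a stated aim.

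- **T0 (WP3).** 44 ALS patients and 40 controls are identified. Patients have clinical and neurophysiological assessment and serum is collected.
- **T1, six months later (WP4).** The heading lists "collection of biological samples and SCFA analysis, and introduction of the diet". The deliverables include "Clinical and neurophysiological assessment of each ALS patient and application of the dietary questionnaire" and "Introduction of a dietary plan".
- **T2 (WP5).** The heading lists "clinical assessment, neurophysiological assessment, collection of biological samples and SCFA analysis". The deliverables place the visit in time: "Clinical and neurophysiological assessment of each ALS patient 6 months after introduction of the diet". No diet item appears.
- **Laboratory (WP6).** "Analysis of stored plasma samples using specific analysis kits", marked as completed, without naming visits.
- **Analysis (WP7).** Three SCFA deliverables are listed, marked Achieved: patients against controls at T0; "Discovery of the SCFAGGYC-PROF profile P-ALS in T0 and T1 evolution"; and a comparison of T2 with T0 in the patients.

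**The concern.** The diet begins at T1, so T1–T2 is the only interval that any patient spends on it, and WP7 does not list a comparison over that interval. The only listed contrast that reaches T2 starts from T0. It therefore combines six months of disease without the diet and six months of disease with it.

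The title itself expects SCFA to be studied for longitudinal effects of disease, so zero change before the diet cannot be taken for granted. If T0–T2 were read as the diet result, pre-diet drift in the same direction as a diet effect would inflate it. Drift in the opposite direction could hide it.

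**Working it through.** **No stated figure to reproduce.** The documents give no alpha, power, effect size, SD or dropout. The visit structure comes from WP3–WP5 and the contrasts from WP7.

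**Step 1: the identity.** For one patient, (T2−T0) = (T1−T0) + (T2−T1).

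| Contrast | Time off diet | Time on diet | Listed in WP7 |
|---|---|---|---|
| T0–T1 | 6 months | 0 | yes |
| T0–T2 | 6 months | 6 months | yes |
| T1–T2 | 0 | 6 months | no |

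The mean T1–T2 change follows by subtracting the two listed mean changes, if the same patients contribute to both. Its confidence interval does not, because that also needs the covariance of the two changes.

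**Step 2: a simple model (hypothetical inputs).** Let SCFA drift by d per six months for reasons other than diet, and let the diet add e. The unit is the SD of a six-month paired change. The expected values are:

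- T1–T2: d + e
- T0–T2: 2d + e
- (T2−T1) minus (T1−T0): (d + e) − d = e

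**Step 3: standard deviations.** Write A = T1−T0 and B = T2−T1, each with variance 1 and covariance c. Then Var(T2−T0) = 2 + 2c and Var(B−A) = 2 − 2c.

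- Equal correlation between visits: c = −0.5, so SD(T2−T0) = 1 and SD(B−A) = √3 = 1.73.
- Independent increments: c = 0, so both SDs are √2 = 1.41.

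**Step 4: probability of p<0.05.** This uses a two-sided paired t test at 0.05 and the noncentral t distribution with noncentrality (mean/SD)·√n. I took n = 44, that is, no loss to follow-up. Ranges span the two correlation cases.

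| d | e | T0–T2 | T1–T2 | (T2−T1) − (T1−T0) |
|---|---|---|---|---|
| 0.1 | 0 | 15–25% | 10% | 5% |
| 0.2 | 0 | 45–74% | 25% | 5% |
| 0.3 | 0 | 79–97% | 49% | 5% |
| −0.2 | 0.5 | 7–10% | 49% | 47–63% |
| 0 | 0.5 | 63–90% | 90% | 47–63% |
| 0.1 | 0.5 | 89–99.5% | 97% | 47–63% |

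Example for the last column with e = 0.5: the noncentrality is 0.5/1.73 × √44 = 1.91 (about 47%) or 0.5/1.41 × √44 = 2.35 (63%).

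**Step 5: fewer completers.** With an assumed 30 pairs, e = 0 and d = 0.2, T0–T2 gives 32–56% and T1–T2 gives 18.5%. For e = 0.5 the difference of changes has noncentrality 0.5/1.73 × √30 = 1.58 or 0.5/1.41 × √30 = 1.94, which is about 33–47% power.

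**The case against.** **WP7 can be read more generously.** Its two longitudinal deliverables together could describe the trajectory over all three visits, and the mean T1–T2 change follows by subtraction. No test or interval is listed for any WP7 contrast, so that omission is not peculiar to T1–T2. This softens the point. It does not remove it, because the last deliverable names its own comparison as T0 against T2 and nothing in WP7 isolates the period after T1.

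**Nowhere is T0–T2 called the diet effect.** A reader might infer that the study presents it so. The documents do not say that; the harm is conditional on that reading.

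**T1–T2 alone is not a clean answer.** This stands. With no diet effect it still gives p<0.05 in 10–49% of trials in the table above. It swaps a larger bias (2d) for a smaller one (d). That is why the T0–T1 change should serve as the within-patient reference.

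**The size is hypothetical.** This also stands. When drift and diet effect point the same way (d = 0.1, e = 0.5), T0–T2 loses little or no power, although it overstates the effect. With no drift, both contrasts expect the same change.

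**The missing T2 questionnaire.** A reader might infer that uptake of the diet was never measured. The documents do not support that. The work packages are deliverable tables, not a schedule of assessments: ALSFRS-R is named only at T0, yet clinical assessment is listed at T1 and T2, and the medical file completed at T2 could hold diet data. What can be said is that a questionnaire given when the plan is introduced cannot describe the following six months, and that the text is silent on diet assessment at T2.

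**Conclusion.** The point holds for the analysis list. WP7 does not list the change over the only on-diet interval, and its one contrast reaching T2 carries six pre-diet months. In the model, T0–T2 differs from the diet-period change by d and from the diet effect by 2d. How much that matters depends on the drift, which the documents do not give. The percentages are illustrations that assume 44 complete pairs, constant drift and one of two correlation patterns.

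No contrast available here isolates a diet effect. No ALS patients without the diet are followed, so the on-diet period coincides with later disease. The difference of changes removes drift only if it is constant across the two intervals. It also gives T1 double weight (T2 − 2·T1 + T0), so error at T1 counts twice. Diet scores at T2, if they exist, would help interpret a result but would not remove this confounding.

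The questionnaire question is a request for clarification and does not carry the point. Change after introducing a dietary plan is a legitimate target without uptake data. The change to WP7 is worth making because it bears on an aim in the title and uses SCFA data already listed.

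**What to change.** 1. Add to WP7 the T1–T2 SCFA change with a confidence interval, in patients with data at both visits.
2. Beside it, report the within-patient difference (T2−T1) minus (T1−T0) with a confidence interval, in patients with data at all three visits, and state the constant-drift assumption.
3. Label both as post hoc, because WP7 is marked Achieved. Give the number of patients in each. Do not present T0–T2 as the diet result.
4. Whether or not T2 diet data exist, describe the T2 result as change following introduction of a dietary plan, confounded with time and disease progression.
5. Clarification only: state whether diet was assessed at T2. If it was, report the T1–T2 change in diet score and its relation to the SCFA change as exploratory. The correlation detectable at 80% power is tanh(2.80/√(n−3)), about 0.41 with 44 pairs and 0.49 with an assumed 30.

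**Cost.** Two further analyses of SCFA data already listed at all three visits, and a narrower conclusion about the diet. The difference of changes is less precise: about 47–63% power for e = 0.5 with 44 pairs, against 90% for T1–T2 when there is no drift. It should therefore accompany T1–T2 and not replace it.

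### No ALS group off the diet is described after T1, so neither the listed T0–T2 change nor a T1–T2 change supports the title's claim of diet effects

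*Combined protocol and SAP*

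**What the plan says.** The title announces "LONGITUDINAL EFFECTS OF DISEASE AND MEDITERRANEAN DIET INTERVENTION". WP3 gives the groups: "Identification of patients with ALS (n=44) and healthy controls (similar age and gender; n=40". The WP4 heading describes "Reassessment of ALS patients after 6 months (visit T1", and its deliverables include "Introduction of a dietary plan". WP5 then lists "Clinical and neurophysiological assessment of each ALS patient 6 months after introduction of the diet".

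WP7 lists three SCFA analyses. One sets the patients against the controls at the first visit: "Discovery of the SCFAGGYC-PROF profile in ALS patients at T0 compared to the control group". Another follows the patients over the off-diet interval, from T0 to T1. The last is the only one that reaches into diet time: "Identification of changes in the dynamics of the SCFAGGYC-PROF profile in ALS patients comparing T0 with T2".

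A T1–T2 contrast is not listed. No randomised, delayed-start or no-diet ALS group is described, and no follow-up visit is described for the controls. The WP4 deliverable does not itself say that every patient starts the diet. That is inferred from the WP4 heading and from the WP5 line on each ALS patient; nothing in the documents suggests that only a subset started.

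**The concern.** From T1 to T2, diet exposure and six further months of ALS coincide in every patient followed. Any SCFA change that the disease would have produced anyway is credited to the diet, or hides a benefit of it. The healthy controls cannot supply the missing course, because they do not have ALS and no later visit is described for them.

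The title also promises effects of disease, so the study itself allows that SCFA levels move with ALS. It cannot then take that movement as zero after T1 without saying so. Adding a T1–T2 test looks like the obvious repair to the listed T0–T2 contrast, but it leaves the same gap. At stake is whether readers are told that the diet changed SCFA levels when the data show only that levels changed while patients were on it.

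**Working it through.** The documents give no alpha, SD, effect size, power or retention, so there is no figure of the plan's to reproduce. The check is algebra on the contrasts, followed by an illustration on assumed values.

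**Contrasts.** Let d1 and d2 be the mean natural change over T0–T1 and T1–T2, and D the diet effect.

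- T1−T0 = d1
- T2−T0 = d1 + d2 + D (listed in WP7)
- T2−T1 = d2 + D (not listed)
- (T2−T1)−(T1−T0) = D + (d2 − d1) (not listed)

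Moving the baseline from T0 to T1 removes d1 and leaves d2. The last contrast equals D only if d1 = d2.

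**False attribution when D = 0.** From the documents: n = 44. Assumed: all 44 seen at all three visits, equal variance, correlation ρ = 0.5 between every pair of visits, a two-sided 5% paired t test, and steady drift d1 = d2 = d in between-patient SD units.

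- SD of any two-visit change = √(2(1−ρ)) = √1 = 1.
- Noncentrality = mean change × √44 / SD, with 43 degrees of freedom. For d = 0.2, T1–T2 gives 0.2 × 6.633 = 1.33, and T0–T2 gives 0.4 × 6.633 = 2.65.

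| Drift per six months | T0–T2 (listed) significant | T1–T2 (not listed) significant |
|---|---|---|
| 0.1 SD | 25.4% | 9.9% |
| 0.2 SD | 73.7% | 25.4% |
| 0.3 SD | 97.3% | 49.4% |

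Sensitivity:

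- At ρ = 0.7 the T1–T2 figures are 13.3%, 38.8% and 70.9%.
- If the SD of the 12-month change is √2 times the six-month SD, the T0–T2 figures fall to 15%, 45% and 79%.
- With 26 patients reaching T2 (assumed), the T1–T2 figures are 8%, 17% and 31%.
- With zero drift every rate is 5%.

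**Precision of the own-control contrast.**

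- Equal correlation between all visits: SD = √(6(1−ρ)), so the ratio to a simple six-month change is √3 = 1.73. At ρ = 0.5 and t = 2.017, the 95% half-widths are 2.017 × 1/6.633 = 0.304 SD and 2.017 × 1.732/6.633 = 0.527 SD.
- Correlation decaying with time (first-order autoregressive): variance = 6 − 8ρ + 2ρ². At ρ = 0.5 the ratio is √(2.5/1.0) = 1.58; at ρ = 0.7 it is √(1.38/0.6) = 1.52.
- With 26 completers and equal correlation 0.5, the half-width is 2.060 × 1.732/√26 = 0.70 SD.

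**Its own weakness.** Suppose a pre-diet drift of 0.3 SD simply stops at T1 and the diet does nothing. The contrast then has mean −0.3 and SD 1.732 (ρ = 0.5), and a 5% test rejects in about 20% of studies.

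**The case against.** The strongest reply has four parts.

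- The patients are observed off the diet from T0 to T1, and WP7 analyses that interval, so the design has an own-control lead-in. This stands. A reader might infer that no ALS patient is ever followed off the diet; that is true only after T1. But WP7 lists no contrast that sets the two intervals against each other.
- WP7 speaks only of changes and never mentions the diet; the causal word is in the title. This also stands. A reader might infer that the analysis plan itself claims a diet effect, and it does not. The wording to change is the title's and that of any report.
- The T0 limit belongs to the SCFA deliverable, while the WP7 objective compares patients with controls without a time limit. That is fair, but no later control visit is described, and controls without ALS could not show its course in any case.
- The rejection rates rest on assumed drift, correlation and retention, and the documents do not say that any SCFA drifts. That is correct, and the rates are illustration only. The algebra does not depend on them.

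A further tempting inference is that the own-control contrast repairs the design, so that an interval excluding zero would establish a diet effect. It would not: d1 = d2 cannot be checked with one interval on each side, and a visit-specific shift at T1, such as an assay batch, enters this contrast twice but T2−T1 only once.

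**Conclusion.** The point holds in limited form. As described, the design supports statements about change while on the diet. It does not support the title's effects of the diet intervention, because no ALS group is described off the diet after T1 and the only listed contrast covering diet time also contains six months without it. This conclusion needs only the contrast algebra and the inference that all ALS patients started the diet at T1.

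The size is conditional: how often a false diet effect would be declared depends on the unknown drift, and on the correlation, retention and test assumed above. The data remain usable; what fails is the causal wording.

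**What to change.** 1. In the title and in any report, replace effects of the diet with changes during the diet period.

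2. In WP7, add the within-patient contrast (T2−T1)−(T1−T0) with its 95% CI, using T0–T1 as each patient's own control. Label it post hoc and exploratory, because WP7 is already marked as achieved.

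3. Beside that result, state that it equals a diet effect only if the natural change would have been the same in both intervals: no curvature, no visit or assay shift, and no selective loss by T2. State that this cannot be checked with one interval on each side, so an interval excluding zero is compatible with a diet effect and does not prove one.

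The cost is wording and one extra contrast on samples already listed as collected; no new patients or visits are needed. The downside is a less favourable claim and a confidence interval about 1.5 to 1.7 times as wide as for a simple six-month change, depending on the correlation structure, and wider still with loss to follow-up.

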### WP6 - Serum analysis to identify serum SCFA levels

WP 6	Objectives: Analysis of stored plasma samples using specific analysis kits	Status
Deliverables	Plasma analysis sheets for the SCFAGGYC-PROF profile through the analysis of stored plasma samples  Data entry into the database	Completed

### WP 7 - Statistical analysis of collected data

WP 7	Objectives: Statistical analysis of clinical, paraclinical and electrophysiological data for each ALS patient compared to the control group	Status
Deliverables	Discovery of the SCFAGGYC-PROF profile in ALS patients at T0 compared to the control group;  Discovery of the SCFAGGYC-PROF profile P-ALS in T0 and T1 evolution;  Identification of changes in the dynamics of the SCFAGGYC-PROF profile in ALS patients comparing T0 with T2.	Achieved

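### Does the lack of a listed dietary measure at T0 or in controls undermine the baseline SCFA comparison between ALS patients and controls?

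*Combined protocol and SAP*

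**What the plan says.** The title gives the aim as "LONGITUDINAL EFFECTS OF DISEASE AND MEDITERRANEAN DIET INTERVENTION". WP3 covers recruitment and T0: "Identification of patients with ALS (n=44) and healthy controls (similar age and gender; n=40"). For T0 data it lists "Clinical and neurophysiological assessment of each ALS patient, with completion of each patient's medical record (including ALSFRS-R"), together with serum sampling. No dietary item appears there, and the assessment line is written for patients only.

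Diet first appears in WP4, the patient visit six months later: "Clinical and neurophysiological assessment of each ALS patient and application of the dietary questionnaire". The WP4 heading puts "collection of biological samples and SCFA analysis, and introduction of the diet" at that same visit and does not say whether the questionnaire came before the diet began. Controls have no listed visit after T0.

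WP7 states its objective as "Statistical analysis of clinical, paraclinical and electrophysiological data for each ALS patient compared to the control group" and names three SCFA deliverables: patients against controls at T0 ("Discovery of the SCFAGGYC-PROF profile in ALS patients at T0 compared to the control group"), patients from T0 to T1, and patients from T0 to T2. It names no test, model or covariate for any of them.

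**The concern.** The study gives a diet and then looks for a change in the SCFA profile, so by its own logic diet can move the outcome. If patients and controls ate differently before T0, the baseline difference in SCFA could come from the disease, from diet or from both. A diet difference could equally hide a disease difference. Comparability in age and gender does not balance diet.

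This is the only one of the three SCFA deliverables that uses the control group, so no other listed comparison can check it. At stake is whether a reported patient-control difference could be read as a feature of ALS.

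**Working it through.** **What is listed, by group and visit**

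| | T0 | T1 | T2 |
|---|---|---|---|
| ALS patients | no dietary item | questionnaire | no dietary item |
| Controls | no dietary item | no visit listed | no visit listed |

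A questionnaire is therefore listed at 1 of 3 patient visits and for 0 of 2 groups at T0.

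**How complete the list is.** WP7 promises a comparison of clinical and electrophysiological data with controls, yet WP3 lists no such assessment of controls. Either those control data were collected and not listed, or the WP7 wording is loose. In both cases, absence from the list is weak evidence that something was not recorded. The contents of the patient file are not given either.

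**Which comparisons are exposed.** The T0-T1 and T0-T2 deliverables compare patients with themselves, so a difference in habitual diet between patients and controls does not enter them. Only the T0 contrast is exposed.

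**Precision of the T0 contrast.** The plan states no alpha, power, SD or effect size, so there is no figure of its own to reproduce. From the group sizes alone, in units of the within-group SD:

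- SE = √(1/44 + 1/40) = 0.218
- 95% half-width = 0.218 × 1.989 (t, 82 df) = 0.435

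**Possible bias (every input assumed).** Let r be the correlation of SCFA with diet and g the group difference in diet in SD. With no disease effect, the spurious difference is r × g.

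- Low end: 0.2 × 0.3 = 0.06 SD
- Middle: 0.5 × 0.5 = 0.25 SD
- High end: 0.5 × 0.8 = 0.40 SD

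At an assumed two-sided alpha of 0.05, the chance of a significant result would be 5.9%, 20.8% and 44.9% respectively, instead of 5%. If g = 0 there is no bias. Nothing in the documents places g anywhere in this range.

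**Precision cost of adjusting for diet.** The variance inflation is 1 + (44 × 40/84) × D²/82, where D is the assumed group difference in diet score in SD. The residual SD is taken as unchanged.

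- D = 0: 1.000, half-width 0.435
- D = 0.5: 1.064, half-width 0.435 × √1.064 = 0.448
- D = 1: 1.256, half-width 0.435 × √1.256 = 0.487

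The cost in precision is small, so the case for or against adjustment turns on validity:

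- Control diet, if not already on file, would have to be recalled after the event.
- Patient diet would come from a questionnaire taken six months after the T0 sample, possibly after the diet had started.
- If the illness alters what patients eat, adjustment removes part of the difference the study set out to describe.

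**The case for a change.** The strongest case for acting is that the worry needs no outside evidence. The study's own premise makes diet a determinant of SCFA, and the groups are not matched on it. A patient record, even one holding dietary notes, would not supply control diet. The top of the assumed range (0.40 SD, about a 45% chance of a false positive) is not trivial, and the cheapest response costs one sentence.

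Much of this stands. The text is read correctly, and on the listed data the T0 contrast is unadjusted for diet. Anyone who attributed it to ALS alone would be going beyond the design.

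What does not stand is the step from there to a defect in the plan. The bias figures come entirely from assumed correlations and diet differences, and no passage suggests that the groups ate differently. The deliverable describes a profile in one group relative to another. The title ties the effects of disease to longitudinal change, which is studied within patients. The cheap responses, a look at the records and a limitation statement, write down what the plan leaves unsaid without altering the design or the analysis. The expensive one, a new questionnaire round in 40 controls, needs re-contact and ethics approval and yields data whose recall and timing errors differ between the groups.

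**Conclusion.** The observation is accurate, but no change to the plan follows. It combines a reporting gap that analysts can be expected to handle sensibly with a trade-off in which adjustment has no clear advantage. If diet was recorded at T0 in both groups, it is available as a supporting analysis. If it was not, the T0 result remains a descriptive group difference unadjusted for diet, and collecting recalled diet now would not reliably improve it.

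The size and direction of any bias cannot be derived from the documents. The illustrative 0.06 to 0.40 SD rests on an assumed SCFA-diet correlation of 0.2 to 0.5 and an assumed diet difference of 0.3 to 0.8 SD. The bias is zero if habitual diets are alike. The conclusion rests on three points: the work-package list is too brief for its silence to count as evidence, the T0 contrast is read as descriptive, and data collection is already marked complete. A report that presented the T0 difference as an effect of ALS alone would be a fault of interpretation, which the plan does not commit.

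### WP7 compares patients with controls only at T0 and measures both changes from T0, so reading these results together can make a chance T0 deviation look like normalisation on the diet

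*Combined protocol and SAP*

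**What the plan says.** WP3 sets the groups: "Identification of patients with ALS (n=44) and healthy controls (similar age and gender; n=40").

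WP7 lists three deliverables:

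- patients against controls: "Discovery of the SCFAGGYC-PROF profile in ALS patients at T0 compared to the control group";
- the first patient change: "Discovery of the SCFAGGYC-PROF profile P-ALS in T0 and T1 evolution";
- the second patient change: "Identification of changes in the dynamics of the SCFAGGYC-PROF profile in ALS patients comparing T0 with T2".

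The WP4 heading places the start of the diet at T1: "Reassessment of ALS patients after 6 months (visit T1): clinical and neurophysiological evaluation, collection of biological samples and SCFA analysis, and introduction of the diet". The WP5 heading covers "Final reassessment of ALS patients (visit T2): clinical assessment, neurophysiological assessment, collection of biological samples and SCFA analysis". Neither work package mentions a repeat control sample.

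The WP7 objective is wider and gives no time point: "Statistical analysis of clinical, paraclinical and electrophysiological data for each ALS patient compared to the control group". No deliverable carries that comparison beyond T0, and none sets T2 against T1. The document gives no significance level, multiplicity rule, SD, within-patient correlation or method of analysis.

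**The concern.** All three deliverables contain the patients' T0 mean. If that mean happens to lie too low, the patient-control difference at T0 is too low, and the T0-T1 and T0-T2 changes are too high by the same error. This is regression to the mean. It does no harm while each contrast is read alone. It matters when a reader asks which analytes were abnormal at T0 and whether they improved by T2, a natural question for a study whose title joins disease effects with a diet intervention.

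At stake is a statement that the profile moved toward normal on the diet when part of the movement comes from the T0 sample. T0-T2 also combines six months before the diet with six months on it. T1-T2, the only interval wholly on the diet, is not listed.

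**Working it through.** The plan has no sample-size or power figure to reproduce. The check below uses a null model with no disease effect and no diet effect.

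**Inputs.** From WP3: 44 patients and 40 controls. Assumed, because the document does not give them: SD 1 in both groups, two-sided 5% tests per analyte with known variance, no dropout, and the same correlation r between any two visits.

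**Step 1: patient-control difference at T0.** Let D = P0 - C.
- Var(D) = 1/44 + 1/40 = 0.0477, so SE = 0.218 SD.
- Significance needs |D| > 1.96 × 0.218 = 0.428 SD.
- The mean |D| among false positives is 2.338 × 0.218 = 0.511 SD.

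**Step 2: link with the T0-T2 change.**
- Var(P2 - P0) = 2(1 - r)/44.
- Cov(D, P2 - P0) = -(1 - r)/44.
- At r = 0.5 the covariance is -0.0114, the variances are 0.0477 and 0.0227, and the correlation is -0.0114/√(0.0477 × 0.0227) = -0.345.

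**Step 3: expected spurious shift.** The patients' share of Var(D) is (1/44)/(1/44 + 1/40) = 40/84 = 0.476. The expected T0-T2 change given D is therefore -(1 - r) × 0.476 × D. At r = 0.5 and D = -0.511 this is 0.5 × 0.476 × 0.511 = 0.12 SD toward controls.

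**Step 4: probabilities after a falsely low T0 result** (from the bivariate normal distribution of D and P2 - P0; simulation agrees within its error).

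| Assumed r | Correlation of D with T0-T2 | Mean shift toward controls | Change points toward controls (nominal 50%) | Significantly so (nominal 2.5%) |
|---|---|---|---|---|
| 0.3 | -0.41 | 0.17 SD | 85% | 13.8% |
| 0.5 | -0.35 | 0.12 SD | 80% | 11.1% |
| 0.7 | -0.27 | 0.07 SD | 74% | 8.4% |
| 0.9 | -0.15 | 0.02 SD | 64% | 5.3% |

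The diet-free T0-T1 change has the same distribution in this model.

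**Step 5: unconditional size.** A false T0 result in either direction (5%) followed by a significant move toward controls has probability 0.05 × 13.8% = 0.7% per analyte at r = 0.3, and 0.05 × 5.3% = 0.3% at r = 0.9.

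**Step 6: if a true gap exists** (assumed, r = 0.5). Given a significant T0 result, the spurious shift is 0.03 SD and the significant rate 3.5% for a true gap of 0.5 SD. For a gap of 0.8 SD they are 0.005 SD and 2.6%.

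**Step 7: T1 as baseline.** Cov(D, P2 - P1) = -r/44 + r/44 up to sign, which is 0. The significant rate after selection on T0 is back at 2.5%. If correlation decays with time, a little remains: with 0.5 over six months and 0.4 over twelve (assumed), the expected T1-T2 shift is (0.5 - 0.4) × 0.476 = 4.8% of the T0 gap, against (1 - 0.4) × 0.476 = 28.6% for T0-T2.

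**Step 8: a tempting rule that fails.** If T1-T2 is tested only when patients differ significantly from controls at both T0 and T1, the rate is about 6.5%, 5.5% and 4.4% for r = 0.3, 0.5 and 0.7. The rule selects on T1, the new baseline.

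**The case against.** The strongest answer is that the premise is not in the plan. WP7 does not say that analytes will be chosen on their T0 result or that change will be called normalisation. Its deliverables concern the whole profile. Without selection, T0-T2 keeps its 5% null rejection rate for every r. This stands, and it limits the point to how results are read together.

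Three stronger readings might be inferred, and the documents do not support them.

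- *The T0-T2 contrast is biased in itself.* It is not, in respect of this mechanism.
- *WP7 rules out any control comparison at T1 or T2.* Its objective names the control group without a time point. The accurate statement is that no such comparison is specified.
- *The study cannot show whether a T0 difference persisted before the diet.* T0-T1 is diet-free and would show the same regression. With the same patients at both visits, (T0 - control) + (T1 - T0) = T1 - control, so the estimate follows from what is listed. What is missing is its standard error, its test and its display.

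Agreement between T0-T1 and T0-T2 is no sign of inflated error either. Two changes from one baseline are correlated, and each keeps its own 5%. They simply do not confirm each other independently.

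The conditional rates also start from a T0 result that is already false. Steps 5 and 6 show how much smaller the problem is otherwise.

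**Conclusion.** The point holds as a caution on interpretation with a cheap remedy, not as a flaw that invalidates a contrast. All three deliverables share the T0 patient values, controls are named only at T0, and no contrast isolates the diet period. Under the null model a falsely low T0 result is followed by a significant T0-T2 move toward controls in about 14% (r = 0.3) to 5% (r = 0.9) of cases, against 2.5%.

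The direction holds for any r below 1. The size rests on the assumed r, equal SDs, equal correlation between visits and no dropout, none of which the document supplies. With a true gap of 0.5 SD or more, or with r near 0.9, the effect is small.

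**What to change.** In WP7, for every analyte and without selection on the T0 result:

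1. Add the T1-T2 patient change as the contrast for the diet period, and base any statement about the diet or normalisation on it rather than on T0-T2.
2. Show the patient-control differences at T1 and T2, with confidence intervals, beside the one at T0, using the existing 40 control values.
3. Do not require significance at both T0 and T1 before testing T1-T2.

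The status column marks WP7 as achieved, so the additions should be reported as made after that analysis.

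**Cost.** Three more contrasts per analyte (T1-T2 and the two control comparisons) on data already held, which adds to the multiplicity that the plan leaves open. Controls were sampled once, so the T1 and T2 comparisons assume stable control levels. One control error also enters all three comparisons: in the null model a false T0 result repeats at T1 in 30%, 39% or 52% of cases for r = 0.3, 0.5 or 0.7, so repetition is weak confirmation. T1-T2 still has no concurrent no-diet group and cannot separate the diet from disease course or time.
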